### 7.4 JUSTIFICATION FOR SENSITIVE PROCEDURES

Placebo control is required to demonstrate unique effects (vs. expectancy effects) of hormones on indices of suicidality.

#### Ongoing Assessment of Suicidality

The PI ([name]) is a clinical psychologist with seven years of experience in risk assessment and empirically supported treatment of chronic suicidality (e.g., Dialectical Behavior Therapy); [name], the consulting clinical psychologist, has over 20 years of experience in risk assessment and treatment of chronic suicidality. The PI and her mentors have also conducted several studies assessing depressive symptoms in women with borderline personality disorder or chronic suicidality, most of which included structured interviews for the assessment of suicidality and other psychiatric symptoms. The available literature indicates that **participants in research studies do not generally become acutely upset in response to the psychological assessments conducted in the present study**. If participants do become upset during an assessment, they will be reminded of their right to discontinue participation, and mood changes or suicidality will be assessed and managed using the **University of Washington Risk Assessment and Management Procedure (UWRAP)**, the suicide risk management protocol recommended by NIH in the context of RCTs for mood disorders.

## 7.5 CONCOMITANT MEDICATIONS, TREATMENTS, AND PROCEDURES

All concomitant prescription medications taken during study participation will be recorded. For this protocol, a prescription medication is defined as a medication that can be prescribed only by a properly authorized/licensed clinician. Medications to be reported are concomitant prescription medications, over-the-counter medications and non-prescription medications.

### 7.5.1 PRECAUTIONARY MEDICATIONS, TREATMENTS, AND PROCEDURES

There are no medications that are prohibited for concomitant use with the study agents, with the exception of any hormonal preparations (that are exclusionary).

## 7.6 PROHIBITED MEDICATIONS, TREATMENTS, AND PROCEDURES

There are no prohibited medications or procedures except hormonal preparations, which are exclusionary.

## 7.7 PROPHYLACTIC MEDICATIONS, TREATMENTS, AND PROCEDURES

Not applicable.

## 7.8 RESCUE MEDICATIONS, TREATMENTS, AND PROCEDURES

Not Applicable.

Hospitalization will serve as a “rescue treatment” should imminent suicidal risk emerge.

## 7.9 PARTICIPANT ACCESS TO STUDY AGENT AT STUDY CLOSURE

Participants will not be provided access to study medications following the termination of this study; as noted above, this is a mechanistic experimental study and not a treatment study.

## 8 ASSESSMENT OF SAFETY

The safety of the study and its participants (as described in 2.3.1) will be monitored via (1) Supervising clinicians [name]. (hormone-related AEs) and [name]. (mood and suicide-related AEs) as well as (2) a Data and Safety Monitoring Board (DSMB).

AEs will be assessed daily during the telephone contacts in the two administration conditions, and will be assessed weekly at laboratory visits. All AEs will be reported immediately to the PI and [name], who will determine severity and next steps in consultation with the appropriate clinical supervisor ([name] for physical adverse events, [name] for psychological and behavioral adverse events).

The DSMB will evaluate AEs that are submitted during scheduled reviews. The North Carolina Translational and Clinical Sciences (NCTraCS) Data and Safety Monitoring Board (NCTraCS DSMB) has agreed to serve in this role. The Board is composed of MDs from a variety of disciplines, an R.N. from the UNC School of Nursing, a Biostatistician, a Regulatory Expert, and for purposes of this study, a psychiatrist or clinical psychologist may serve as an ad hoc member.

Although not expected given the doses and duration of hormone exposure, the DSMB will, during scheduled reviews, specifically evaluate the frequency of AEs related to the hormonal RCT. The DSMB will specify the tables and data it wishes to have presented to it at all meetings, including but not limited to, moderate to severe side effects and all serious adverse events. **DSMB review of this study will occur every six months.** At these meetings the DSMB will also review data from participants who have been discontinued by study staff or who have withdrawn or dropped out of the study, and the reasons for discontinuation. The DSMB will also identify if any study procedures should be altered or stopped in the event of an indication of harm to participants attributable to the study interventions. The DSMB will evaluate issues of participant safety as well as the adequacy and integrity of accumulating data, review of enrollment data, and making recommendations regarding safety.

## 8.1 SPECIFICATION OF SAFETY PARAMETERS

### 8.1.1 DEFINITION OF ADVERSE EVENTS (AE)

**Adverse event** means any untoward medical occurrence associated with the use of an intervention in humans, whether or not considered intervention-related (21 CFR 312.32 (a)).

### 8.1.2 DEFINITION OF SERIOUS ADVERSE EVENTS (SAE)

**Serious adverse event or serious suspected adverse reaction.** An AE or suspected adverse reaction is considered "serious" if, in the view of either the investigator or sponsor, it results in any of the following outcomes: death, a life-threatening adverse event, inpatient hospitalization or prolongation of existing hospitalization, or a persistent or significant incapacity. Important medical events that may not result in death, be life-threatening, or require hospitalization may be considered serious when, based upon appropriate medical judgment, they may jeopardize the patient or subject and may require medical intervention to prevent one of the outcomes listed in this definition.

**\*Notable examples of serious adverse events in the present study include development of a venous thromboembolism or suicide attempt.**

### 8.1.3 DEFINITION OF UNANTICIPATED PROBLEMS (UP)

OHRP considers unanticipated problems involving risks to participants or others to include, in general, any incident, experience, or outcome that meets all of the following criteria:

- Unexpected in terms of nature, severity, or frequency given (a) the research procedures that are described in the protocol-related documents, such as the IRB-approved research protocol and informed consent document; and (b) the characteristics of the participant population being studied;
- Related or possibly related to participation in the research (“possibly related” means there is a reasonable possibility that the incident, experience, or outcome may have been caused by the procedures involved in the research); and
- Suggests that the research places participants or others at a greater risk of harm (including physical, psychological, economic, or social harm) than was previously known or recognized.

This study will use the OHRP definition of UP.

## 8.2 CLASSIFICATION OF AN ADVERSE EVENT

### 8.2.1 SEVERITY OF EVENT

For AEs not included in the protocol defined grading system, the following guidelines will be used to describe severity.

- **Mild** – Events require minimal or no treatment and do not interfere with the participant's daily activities.
- **Moderate** – Events result in a low level of inconvenience or concern with the therapeutic measures. Moderate events may cause some interference with functioning.
- **Severe** – Events interrupt a participant's usual daily activity and may require systemic drug therapy or other treatment. Severe events are usually potentially life-threatening or incapacitating.

### 8.2.2 RELATIONSHIP TO STUDY AGENT

For all AEs, Drs. [name] and [name] will urgently collaborate with appropriate clinical supervisors ([name] for physical/medical events, [name] for behavioral/psychological events) to determine the AE's causality based on temporal relationship and his/her clinical judgment. The degree of certainty about causality will be graded using the categories below.

**Definitely Related** – There is clear evidence to suggest a causal relationship, and other possible contributing factors can be ruled out. The clinical event occurs in a plausible time relationship to drug administration and cannot be explained by concurrent disease or other drugs or chemicals. The response to withdrawal of the drug (dechallenge) should be clinically plausible. The event must be pharmacologically or phenomenologically definitive, with use of a satisfactory rechallenge procedure if necessary.

**Probably Related** – There is evidence to suggest a causal relationship, and the influence of other factors is unlikely. The clinical event occurs within a reasonable time after administration of the drug, is unlikely to be attributed to concurrent disease or other drugs or chemicals, and

follows a clinically reasonable response on withdrawal (dechallenge). Rechallenge information is not required to fulfill this definition.

**Possibly Related** – There is some evidence to suggest a causal relationship (e.g., the event occurred within a reasonable time after administration of the trial medication). However, other factors may have contributed to the event (e.g., the participant's clinical condition, other concomitant events). Although an AE may rate only as "possibly related" soon after discovery, it can be flagged as requiring more information and later be upgraded to "probably related" or "definitely related," as appropriate.

**Unlikely to be related** – A clinical event whose temporal relationship to drug administration makes a causal relationship improbable (e.g., the event did not occur within a reasonable time after administration of the trial medication) and in which other drugs or chemicals or underlying disease provides plausible explanations (e.g., the participant's clinical condition, other concomitant treatments).

**Not Related** – The AE is completely independent of study drug administration, and/or evidence exists that the event is definitely related to another etiology. There must be an alternative, definitive etiology documented by [name] or [name].

### 8.2.3 EXPECTEDNESS

Drs. [name] and [name] will collaborate with appropriate clinical supervisors ([name] for physical/medical, [name] for psychological/behavioral) to make determinations about whether an AE is expected or unexpected. An AE will be considered unexpected if the nature, severity, or frequency of the event is not consistent with the risk information previously described for the study agent.

## 8.3 TIME PERIOD AND FREQUENCY FOR EVENT ASSESSMENT AND FOLLOW-UP

The occurrence of an AE or SAE may come to the attention of study personnel during study visits and interviews of a study participant. All AEs including local and systemic reactions not meeting the criteria for SAEs will be captured on the appropriate documentation. Information to be collected includes event description, time of onset, clinician's assessment of severity, relationship to study product (assessed only by those with the training and authority to make a diagnosis), and time of resolution/stabilization of the event. All AEs occurring while on study must be documented appropriately regardless of relationship. All AEs will be followed to adequate resolution.

Pre-existing medical conditions are exclusionary for participation in the trial, with the exception of psychiatric conditions. Any psychiatric condition or symptom that is present at the time that the participant is screened, including mood symptoms and suicidal *ideation*, will be considered as baseline and not reported as an AE. However, if the study participant's condition or symptom deteriorates significantly with regard to the severity or impact of the symptom on the participant's functioning or safety (as determined by Drs. [name], [name], [name], and [name]) at any time during the study, it will be recorded as an AE.

UPs will be recorded in the data collection system throughout the study.

Changes in the severity of an AE will be documented to allow an assessment of the duration of the event at each level of severity to be performed. AEs characterized as intermittent require documentation of onset and duration of each episode.

The PI will record all reportable events with start dates occurring any time after informed consent is obtained until 7 (for non-serious AEs) or 30 days (for SAEs) after the last day of study participation. At each phone call and study visit, study staff will inquire about the occurrence of AE/SAEs since the last visit. All AEs will be immediately (within 2 hours) reported to the PI, who will consult with Drs. [name], [name], and [name] in the 24 hours that follow. Events will be followed for outcome information until resolution or stabilization.

## 8.4 REPORTING PROCEDURES

### 8.4.1 ADVERSE EVENT REPORTING

Study staff will screen for all AEs at each telephone call and study visit. [name] or [name] will be on call for all visits and telephone calls to ensure that emergent mood deterioration or suicide risk can be immediately handled by a licensed clinical psychologist with experience in suicide risk assessment ([name] or [name]) using the LRAP/UWRAP protocol (the tool recommended by NIH for clinical trials with suicidal subjects). Medical/physical AEs will be discussed as soon as possible, and within the following 24 hours, with Drs. [name] and [name].

The PI [name] (in consultation with Drs. [name], [name], and [name]) will review all protocol data at weekly meetings, including enrollment and retention statistics and aggregate reports of side effects/AEs. As the contact PI, [name] will be the one responsible for reporting any severe AEs to the IRB and DSMB within 1 week. Since we are employing a marketed pharmaceutical product (i.e., a non-IND study), unexpected Serious AEs will be also be reported to the FDA Medwatch Program. The NIMH program officer will be notified of any study modifications or suspension imposed by the DSMB or local IRB in response to an AE.

### 8.4.2 SERIOUS ADVERSE EVENT REPORTING

The PI ([name]) will complete a SAE Form within the following timelines:

- All deaths and immediately life-threatening events, whether related or unrelated, will be recorded on the SAE Form and submitted to the DCC/study sponsor within 24 hours of site awareness. See **Section 1, Key Roles** for contact information.

All SAEs will be followed until satisfactory resolution or until the PI deems the event to be chronic or the adherence to be stable. Other supporting documentation of the event may be requested by the DSMB or study sponsor and will be provided as soon as possible. The study sponsor will be responsible for notifying FDA of any unexpected fatal or life-threatening

suspected adverse reaction as soon as possible but in no case later than 7 calendar days after the sponsor's initial receipt of the information.

#### 8.4.3 UNANTICIPATED PROBLEM REPORTING

Incidents or events that meet the OHRP criteria for UPs require the creation and completion of an UP report form. It is the site investigator's responsibility to report UPs to their IRB and to the study sponsor. The UP report will include the following information:

- Protocol identifying information: protocol title and number, PI's name, and the IRB project number;
- A detailed description of the event, incident, experience, or outcome;
- An explanation of the basis for determining that the event, incident, experience, or outcome represents an UP;
- A description of any changes to the protocol or other corrective actions that have been taken or are proposed in response to the UP.

To satisfy the requirement for prompt reporting, UPs will be reported using the following timeline:

- All UPs will be reported to the IRB, the DSMB, and to the study sponsor within 1 week of the investigator becoming aware of the event.

#### 8.4.4 EVENTS OF SPECIAL INTEREST

Not applicable.

#### 8.4.5 REPORTING OF PREGNANCY

Pregnancy will result in immediate withdrawal from the study and a breaking of the blind to [name]; [name] will oversee appropriate clinical care, including supervised hormonal discontinuation.

### 8.5 STUDY HALTING RULES

At six month intervals, the study biostatistician ([name]) will test whether there are significant differences in the occurrence of moderate, severe, and serious AEs in the placebo vs. the experimental condition with alpha set at .05. These results will be provided to DSMB along with the summary report of enrollment.

Administration of study agent will be halted when three serious AEs\* determined to be "probably related" are observed. The PI will immediately notify the DSMB when this occurs. The DSMB will notify the study sponsor and investigators immediately when the third severe event is reported and enrollment screens will stop accepting new study participants. [name] will again perform an unblinded statistical analysis to further determine whether active study medication (E2/P4) is significantly related to greater risk of AEs relative to placebo. All requested documentation will be provided to the DSMB. The DSMB will convene an ad hoc meeting by teleconference or in writing as soon as possible. The DSMB will provide recommendations for

proceeding with the study to the PI and the NIH. The study sponsor will inform all appropriate regulatory agencies of the temporary halt and the disposition of the study.

The DSMB will consider stopping the entire study based on the results of the statistical tests provided by [name]: specifically, if the experimental hormone stabilization condition is associated with greater risk of severe or serious AEs than placebo, and there is evidence (as determined by [name]) that such AEs are causally related to the study drug, the study will be terminated.

**\*Notable examples of serious adverse events in the present study include development of a venous thromboembolism or suicide attempt.**

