#### 5.4.2 HANDLING OF PARTICIPANT WITHDRAWALS OR TERMINATION

**Protocol for Discontinuation and Referral.** If a participant shows emergence of severe mood symptoms or greater than low risk of suicide attempt, the UWRAP protocol for assessing and managing suicide risk will be closely followed, supervised by [name] and [name] (see Appendix for UWRAP). However, if a participant is judged to be at imminent risk of suicide and therefore in need of immediate hospitalization, the participant will be immediately discontinued from participation and hospitalized. Our offices are in close proximity to UNC emergency department, and participants requiring immediate emergency care can easily be transferred there. An immediate follow-up phone call to the participant's mental health provider alerting them to the change in symptoms (see information below regarding consent to provider-researcher communication) will occur immediately. If the participant is taking study medication currently, [name] will immediately be contacted and he will break the blind. If it is revealed that the participant is currently in the placebo condition, he will take no further action. However, if it is revealed that the participant was currently in an active hormone stabilization condition, he will oversee the subject's discontinuation of the exogenous hormone according to his best clinical judgment.

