#### 10.4.7 PLANNED INTERIM ANALYSES

##### 10.4.7.1 SAFETY REVIEW

At six month intervals, the study biostatistician ([name]) will test whether there are significant differences in the occurrence of moderate, severe, and serious AEs in the placebo vs. the experimental condition with alpha set at .05. These results will be provided to DSMB along with the summary report of enrollment.

Administration of study agent will be halted when three serious AEs\* determined to be “probably related” are observed. The PI will immediately notify the DSMB when this occurs. The DSMB will notify the study sponsor and investigators immediately when the third severe event is reported and enrollment screens will stop accepting new study participants. [name] will again perform an unblinded statistical analysis to further determine whether active study medication (E2/P4) is significantly related to greater risk of AEs relative to placebo. All requested documentation will be provided to the DSMB. The DSMB will convene an ad hoc meeting by teleconference or in writing as soon as possible. The DSMB will provide recommendations for proceeding with the study to the PI and the NIH. The study sponsor will inform all appropriate regulatory agencies of the temporary halt and the disposition of the study.

The DSMB will consider stopping the entire study based on the results of the statistical tests provided by [name]: specifically, if the experimental hormone stabilization condition is associated with greater risk of severe or serious AEs than placebo, and there is evidence (as determined by follow up with [name] using unblinded data provided by [name]) that such AEs are causally related to the study drug, the study will be terminated.

**\*Notable examples of serious adverse events in the present study include development of a venous thromboembolism or suicide attempt.**

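### After the three-event halt, termination is tied to a significance test that three serious AEs would usually fail even if all three occurred on active agent; the halt clause, the termination clause and the DSMB's general remit need reconciling

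*Combined protocol and SAP*

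**What the plan says.** The same rule stands in Sections 5.5, 8.5 and 10.4.7.1, with small differences in wording. It has four parts.

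- **Six-monthly test.** The biostatistician compares moderate, severe and serious AEs, "placebo vs. the experimental condition with alpha set at .05".
- **Halt.** "Administration of study agent will be halted when three serious AEs" graded probably related have been observed. Screening also stops accepting new participants.
- **Analysis after the halt.** The biostatistician again runs an analysis, unblinded, of whether active agent is "significantly related to greater risk of AEs relative to placebo". Alpha is not restated. No test, sidedness or event set is given.
- **Termination.** "The DSMB will consider stopping the entire study based on the results of the statistical tests", and the condition is spelled out: "specifically, if the experimental hormone stabilization condition is associated with greater risk of severe or serious AEs than placebo", joined by an *and* to evidence that the events are causally related to study drug. If both hold, the study will be terminated.

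Section 10.4.4 scores each AE yes or no, once per woman per condition. Section 10.4.1 describes a two-period crossover and states two-tailed testing at .05, but only for the primary hypotheses. Section 10.5 plans 45 women enrolled and 30 completing. Section 8 separately lets the DSMB identify procedures to alter or stop on an indication of harm, with no reference to a p-value.

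**The concern.** The halt is set at a count that a significance test can hardly use. A test on three events has almost no room to reach .05, yet the termination clause makes the test result one of two conditions that must both be met. Suppose three women had a thromboembolism or a suicide attempt, which are the protocol's own examples of serious AEs, all on active agent and all judged causal. The causality condition would be satisfied and the statistical one would usually not be. Under Section 8 the same facts look like an indication of harm. The protocol does not say which provision governs.

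There is a second, conditional problem. Section 5.4.2 says that if a woman is judged at imminent risk of suicide and in need of immediate hospitalization, "the participant will be immediately discontinued from participation and hospitalized". If that happens in condition 1, she has no second condition. A test restricted to complete pairs would drop her event.

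**Working it through.** **Plan's own figure.** The documents give no p-value, power or other operating characteristic for this rule, so there is none to reproduce.

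**Inputs.** Halt at three serious AEs (8.5); alpha .05 (8.5, six-monthly test, carried over by inference to the analysis after the halt); yes/no scoring per woman per condition (10.4.4); 30 completers and 45 enrolled (10.5). Assumption: the three triggering events are the only severe or serious AEs and fall in three different women.

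**Most extreme split: 3 on active, 0 on placebo.**

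- Exact McNemar, one-sided: 0.5³ = .125. Two-sided: 2 × .125 = .25.
- Uncorrected McNemar: z = (3 − 0)/√(3 + 0) = 1.73, giving .083 two-sided and .042 one-sided.
- Fisher, one-sided: C(n,3)/C(2n,3). For n = 30, 4060/34220 = .119. For n = 45, 14190/117480 = .121. Doubling gives .237 and .242.
- Pearson, n = 30: pooled risk 3/60 = .05; z = 0.10/√(.05 × .95 × 2/30) = 1.78, giving .076 two-sided.

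| Test, 3 v 0 | Two-sided p | One-sided p |
|---|---|---|
| Exact McNemar | .25 | .125 |
| McNemar, continuity-corrected | .248 | .124 |
| McNemar, mid-p | .125 | .0625 |
| McNemar, uncorrected | .083 | .042 |
| Fisher, n = 30 / 45 per condition | .237 / .242 | .119 / .121 |
| Pearson, n = 30 / 45 | .076 / .078 | .038 / .039 |
| Barnard, n = 30 / 45 | .093 / .092 | .046 / .046 |

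Every two-sided entry exceeds .05. Exact McNemar and Fisher also fail one-sided. Only one-sided uncorrected McNemar, Pearson and Barnard pass.

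**How many events would be enough, two-sided exact tests.** For k v 0, exact McNemar is 2 × 0.5^k.

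| Split | Exact McNemar | Fisher, n = 30 to 45 |
|---|---|---|
| 3 v 0 | .25 | .24 |
| 4 v 0 | .125 | .11 to .12 |
| 5 v 0 | .0625 | .052 to .056 |
| 6 v 0 | .031 | .024 to .026 |

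So 6 v 0 is needed, twice the halt count. With one woman discordant the other way, exact McNemar needs 8 v 1 (.039); 7 v 1 gives .070.

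**Sensitivity to the choice of test.** Exact McNemar one-sided passes at 5 v 0 (.031). Uncorrected McNemar two-sided passes at 4 v 0 (.0455). Unpaired tests can pass at three events when exposure is very small or very unequal: Fisher 3/10 v 0/20 gives .030, and two-sided Pearson with 6 per condition gives .0455.

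**Effect of once-per-woman scoring.** If two of the three serious AEs occur in one woman in one condition, they may count once. The split is then 2 v 0, with exact two-sided p = 2 × 0.5² = .50.

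**The case against.** A reader might infer that three events can never be significant, or that the termination clause can never be met. The documents do not support either reading.

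- **The test is not named.** Two-tailed testing is stated only for the primary hypotheses, and the clause itself is directional. A one-sided approximate or unconditional test passes at 3 v 0. This stands, and limits the claim to two-sided tests and to exact McNemar and Fisher. It also means that an unspecified choice of test could decide whether the statistical condition is met.
- **The .05 level is inferred.** It is attached to the six-monthly test, and the termination sentence speaks of association without the word significant. The inference is reasonable: the preceding analysis asks about significance, is described as a repeat by the same biostatistician, and its results are named as the basis for stopping. It remains an inference.
- **The event sets differ.** The trigger counts serious AEs graded probably related. The termination comparison covers severe or serious AEs without restriction on grading. More than three events may be in the analysis at the halt, and six on active with none on placebo would pass. This stands.
- **The DSMB is not confined to the p-value.** It convenes ad hoc, receives all documentation it requests, makes its own recommendations (8.5), sees AE tables by condition (10.4.4), and may act on an indication of harm (8). Agent and screening are already stopped at the third event, so the rule does not keep anyone on agent because a test failed. This stands and lowers the severity. It does not remove the conflict between an explicit termination criterion and a broader remit.
- **No paired AE test is specified.** The loss of women discontinued in condition 1 is therefore a risk only if complete pairs are used.

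**Conclusion.** The rule is wrong as written and should be fixed, but it is not a failure that leaves participants unprotected. If the three triggering events are the only severe or serious AEs, the termination clause would usually be unmet at the moment it is invoked, even with every event on active and every event judged causal: two-sided p runs from .076 to .25 across the tests tabulated, and two-sided exact tests need 6 v 0. This rests on reading the analysis after the halt as a .05 test, on 30 to 45 women exposed per condition, and on no other severe or serious AEs. Relaxing any of these can change the result, so the claim is a mismatch between the halt trigger and the termination criterion, not an impossibility.

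**What to change.** In Sections 5.5, 8.5 and 10.4.7.1, reconcile the halt clause, the termination clause and the DSMB remit in Section 8, so that a non-significant test on a handful of events is neither a bar to termination nor read as evidence of safety.

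For severe and serious AEs, give the DSMB the unblinded number of women with events by condition at onset, over all women exposed in that condition, with an exact confidence interval alongside the causality review. Include women whose event ended participation in condition 1.

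If a test is kept, name the test, its sidedness, its alpha and the event set, including which causality grades count.

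The halt threshold and the decisions to stop or resume remain with the sponsor and DSMB.

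The cost is wording in three copies of one rule and a change to the DSMB table shell; no participants or procedures are added. The downside is that the DSMB relies on judgement rather than on a p-value.
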